### Visit 1 (Day 0)

Tasks to be performed prior to randomization and vaccination:

- Re-check inclusion/exclusion criteria
- Check of safety laboratory results obtained at Screening Visit
- Targeted physical examination, including auscultation of heart and lungs, see [Section 8.2.3](#) for more details
- Evaluation of vital signs
- Recording of baseline signs and symptoms
- Questions on cardiac signs and symptoms
- Review of prior/concomitant medications
- Assessment of axillary and supraclavicular lymphadenopathy, see [Section 8.2.3](#) for more details
- Examination of the possible deltoid vaccination sites
- Counseling on avoidance of contact spread (specifically after ACAM2000® vaccination), HIV infection and pregnancy
- Urine or serum pregnancy test (5 ml, if applicable)
- Blood draw (serum collection) for antibody analysis (16 ml)

Blood draws and all other tasks mentioned above must always be performed prior to vaccination. If the subject is still eligible for participation in this trial, the subject will be randomized. The following tasks will be performed after randomization:

- Vaccination: Group 1: administration of one (1) dose of MVA-BN®  
Group 2: administration of one (1) dose of ACAM2000®
- Subject observation by clinical trial site staff for at least 30 minutes after vaccination

### Visit 1 (Day 0)

- Examination of the vaccination site and/or the area around the bandage for skin reactions (approximately 30 minutes after vaccination)
- Recording of immediate AEs/SAEs/AESIs
- Handout of memory aid, ruler and thermometer
- Bandage application and handout of clinical trial specific Care Kits to Group 2 subjects only
- After ACAM2000® scarification subjects should change their own bandage as instructed by the administering clinic (leave the bandage on for the 1st 48 hours, then change every day or when bandage becomes wet) using the clinical trial specific Care Kits provided by site staff

**Temporary deferral of vaccination:** If an acute illness is present at the time scheduled for the vaccination, the subject may be vaccinated at a later date within the foreseen time window. The vaccine can be administered to persons with a minor illness such as diarrhea, mild upper respiratory infection, or any other mild condition with or without low-grade febrile illness, i.e. oral temperature < 100.4°F (< 38.0°C).

### Visit 2 (Visit 1 + 6-8 days)

The following tasks will be performed

- Targeted physical examination, including auscultation of heart and lungs (if clinically indicated); see [Section 8.2.3](#) for more details
- Evaluation of vital signs
- Counseling on avoidance of contact spread (specifically after ACAM2000® vaccination), HIV infection and pregnancy
- Assessment of axillary and supraclavicular lymphadenopathy; see [Section 8.2.3](#) for more details
- Examination of vaccination site
- Recording of AEs/SAEs/AESIs
- Review of memory aid
- Blood draw (serum collection) for antibody analysis (16 ml)

Group 2 only:

- Photo of vaccination site
- Bandage application/change

### Visit 3 (Visit 1 + 13-15 days)

The following tasks will be performed

- Targeted physical examination, including auscultation of heart and lungs; see [Section 8.2.3](#) for more details
- Evaluation of vital signs
- Perform ECG
- Questions on cardiac signs and symptoms
- Review of prior/concomitant medications
- Counseling on avoidance of contact spread (specifically after ACAM2000® vaccination), HIV infection and pregnancy
- Examination of the vaccination site
- Assessment of axillary and supraclavicular lymphadenopathy; see [Section 8.2.3](#) for more details
- Recording of AEs/SAEs/AESIs
- Collection of the memory aid and review with subject
- Blood draw for safety laboratory (CBC with differential, total bilirubin, Alk Phos, AST, ALT, creatinine, sodium, potassium and calcium, 10 ml) including troponin I testing
- Blood draw (serum collection) for antibody analysis (16 ml)
- If vaccination site has not yet fully healed then a memory aid extension would be handed out

Group 2 only:

- Photo of vaccination site
- Bandage application/change

#### Visit 4 (Visit 1 + 27-29 days)

The following tasks will be performed

- Targeted physical examination, including auscultation of heart and lungs; see [Section 8.2.3](#) for more details
- Evaluation of vital signs
- Questions on cardiac signs and symptoms
- Review of prior/concomitant medications
- Counseling on avoidance of contact spread (specifically after ACAM2000® vaccination), HIV infection and pregnancy. **Group 2:** Counseling for avoidance of pregnancy not required.
- Assessment of axillary and supraclavicular lymphadenopathy; see [Section 8.2.3](#) for more details
- Examination of vaccination site
- Urine or serum pregnancy test (5 ml, if applicable)
- Recording of AEs/SAEs/AESIs
- Blood draw (serum collection) for antibody analysis (16 ml)
- If a memory aid extension had been provided at Visit 3 then a review of the memory aid extension should be conducted and the memory aid collected

Group 1:

Tasks mentioned above must always be performed or repeated prior to vaccination

- Second administration of one (1) dose of MVA-BN®
- Subject observation by clinical trial site staff for at least 30 minutes after vaccination
- Handout of memory aid
- Recording of immediate AEs/SAEs/AESIs

**Temporary deferral of vaccination:** If an acute illness is present at the time scheduled for the vaccination, the subject may be vaccinated at a later date within the foreseen time window. The vaccine can be administered to persons with a minor illness such as diarrhea, mild upper respiratory infection, or any other mild condition with or without low-grade febrile illness, i.e. oral temperature < 100.4°F (< 38.0°C).

**Visit 4 (Visit 1 + 27-29 days)**

Group 2:

- If vaccination site has not yet fully healed then another memory aid extension would be handed out.
- Bandage application/change

**All subsequent visits are relevant for Group 1 subjects only.**

**Visit 5 (Group 1: Visit 4 + 6-8 days)**

The following tasks will be performed

- Targeted physical examination, including auscultation of heart and lungs (if clinically indicated); see [Section 8.2.3](#) for more details
- Evaluation of vital signs
- Counseling on avoidance of HIV infection and pregnancy
- Assessment of axillary and supraclavicular lymphadenopathy; see [Section 8.2.3](#) for more details
- Recording of AEs/SAEs/AESIs
- Examination of vaccination site
- Review of memory aid

**Visit 6 (Group 1: Visit 4 + 13-15 days)**

The following tasks will be performed

- Targeted physical examination, including auscultation of heart and lungs; see [Section 8.2.3](#) for more details
- Evaluation of vital signs
- Perform ECG (if clinically indicated)
- Questions on cardiac signs and symptoms
- Review of prior/concomitant medications

**Visit 6 (Group 1: Visit 4 + 13-15 days)**

- Counseling on avoidance of HIV infection and pregnancy
- Examination of the vaccination site
- Assessment of axillary and supraclavicular lymphadenopathy; see [Section 8.2.3](#) for more details
- Collection of the memory aid handed out at Visit 4 and review with subject
- Recording of AEs/SAEs/AESIs
- Blood draw (serum collection) for antibody analysis (16 ml)
- Blood draw for safety laboratory (CBC with differential, total bilirubin, Alk Phos, AST, ALT, creatinine, sodium, potassium and calcium, 10 ml)

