  - 7 If lesion at vaccination site has not healed at Day 14, measurements of lesion size, erythema and induration should be recorded on a memory aid extension each day until healed or Visit 4.
  - 8 WOCBP only. At Screening Visit, a serum test must be performed. At all other visits, either a serum or urine pregnancy test will be performed.
  - 9 Approximate volumes of single blood draws: Safety lab including all tests: 22 ml at SCR (incl. serum for pregnancy test) and 10 ml at regular visits, 5 ml for serum pregnancy test and 16 ml for antibody analysis.

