Subjects receiving MVA-BN® may have the vaccination site covered with a BAND-AID® or equivalent as needed. Subjects receiving ACAM2000® will have the vaccination site covered with a semi-permeable bandage provided in a Care Kit (the contents of which will be defined in agreement with the trial site staff and will be the same for all ACAM2000® vaccinated subjects). The vaccination site must be kept covered for 30 days and/or until the site is healed. The vaccinee

should change the bandage as instructed by the administering clinic (leave the bandage on for the 1st 48 hours, then change every day or when bandage becomes wet) until the vaccination site scab falls off as this will keep the vaccination site intact and will minimize softening. Salves or ointments must not be applied to the vaccination site.

Any AEs that occur during or after vaccination will be recorded. All subjects will be asked to record, on a subject memory aid, daily maximum temperatures and solicited AEs for 15 days, beginning with the day of vaccination and report them to the research staff. If solicited AEs persist after 14 days post vaccination, daily symptoms and temperatures will continue to be measured each day until resolved or Visit 10 (Group 1) or Visit 4 (Group 2) respectively.

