**Visit 10 (Visit 7 + 27-29 days)**

- Examination of the vaccination site
- Bandage application/change
- Assessment of axillary and supraclavicular lymphadenopathy; see [Section 8.2.3](#) for more details
- Recording of AEs/SAEs/AESIs
- Urine or serum pregnancy test (5 ml, if applicable)
- Blood draw (serum collection) for antibody analysis (16 ml)
- If a memory aid extension had been provided at Visit 9 then a review of memory aid extension should be conducted and the memory aid collected

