**4.2.3 Follow Up Phase**

**Visit 5 (Group 2: Visit 1 + 41-43 days)**

**The following tasks will be performed**

- Blood draw (serum collection) for antibody analysis (16 ml)

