#### **8.1.3.2 Solicited Adverse Events**

Within this CTP solicited AEs are defined as all symptoms specifically listed in the memory aid provided to the subjects following each vaccination. The subjects are requested to monitor and record local symptoms (i.e. pain, redness (erythema), swelling, induration, itching (pruritus) and

vaccination site appearance (normal/healed, red spot, bump, reddish blister, whitish blister, scab, ulcer/crater, warmth, swollen >3in, red streaks, drainage) as well as general symptoms (i.e. body temperature, headache, muscle pain (myalgia), chills, nausea, fatigue, malaise, swollen lymphnodes) in the memory aid daily for the day of vaccination and the following 14 days (days 0-14, 15 day period). Any symptoms persisting beyond Day 14 post vaccination are recorded in a memory aid extension. The definition of AEs originates from the MVA-BN® Investigator's Brochure and the ACAM2000® Prescribing Information ([Appendix IVc](#); [Section 17.7](#)).

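### The protocol contradicts itself on diary follow-up of solicited reactions lasting beyond Day 14, and the SAP does not say over which window their durations are computed

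*Protocol*

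**What the plan says.** **General text.** Protocol Section 8.1.3.2 states: "Any symptoms persisting beyond Day 14 post vaccination are recorded in a memory aid extension". It names no particular dose. Section 4.2.2 says that "daily symptoms and temperatures will continue to be measured each day until resolved or Visit 10 (Group 1) or Visit 4 (Group 2) respectively". Section 8.2.6 and schedule footnote 6 set the same end points.

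**Visit lists and schedule (Protocol Sections 4.2.2 and 1.5).**
- *MVA-BN dose 1.* The Visit 3 list, which covers both groups, says: "If vaccination site has not yet fully healed then a memory aid extension would be handed out". The Visit 4 list collects it. The Group 1 schedule marks neither step.
- *MVA-BN dose 2.* At Visit 6 the only diary task is "Collection of the memory aid handed out at Visit 4 and review with subject". No extension is handed out, and Visit 7 has no diary review or collection. The schedule agrees.
- *ACAM2000, Group 1.* An extension is issued at Visit 9 and returned at Visit 10: "If a memory aid extension had been provided at Visit 9 then a review of memory aid extension should be conducted".
- *ACAM2000, Group 2.* An extension is issued at Visit 3 and returned at Visit 4. The Visit 4 list then adds: "If vaccination site has not yet fully healed then another memory aid extension would be handed out". Footnote 7 of the Group 2 schedule stops earlier: measurements "should be recorded on a memory aid extension each day until healed or Visit 4". Visits 5 and 6 in Group 2 consist of an antibody blood draw only.
- *Trigger.* In the visit lists and in footnote 7, the extension depends on an unhealed site. Footnote 7 covers lesion size, erythema and induration.

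**Analysis.** Duration of solicited local and general reactions is part of the secondary endpoints (Protocol Section 9.3.2, Days 0-14). SAP Section 3.8.3 computes it as end date minus start date plus one, and computes nothing if the event is ongoing at the end date. SAP Section 3.10.9 summarises it by mean, SD, median and range. Tables 15.3.1.2.2 and 15.3.1.3.2 carry a 15-day follow-up label.

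**The concern.** Comparing the reactogenicity of MVA-BN, ACAM2000 alone and ACAM2000 after MVA-BN is a secondary objective, and duration is one of its measures. A comparison of durations needs the same observation window in each period, or an explicit treatment of reactions that outlast it. Here the instructions that site staff work from differ by dose and group, and they differ from the general rule. The SAP rule of leaving out ongoing events makes this matter: where the diary stops at Day 14, the longest reactions are the ones likely to lack an end date and fall out of the mean and median. Where the diary runs on, the same reactions are counted with their long durations.

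**Working it through.** **Standard diary.** Days 0 to 14 inclusive: 14 − 0 + 1 = 15 days. This agrees with the protocol and with the label on the SAP tables.

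**Visit timing (Protocol Section 1.5).** Visit 4 = Visit 1 + 27-29 days; Visit 7 = Visit 1 + 55-57; Visit 10 = Visit 7 + 27-29. In Group 2, Visit 4 = Visit 1 + 27-29.

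**Diary window after each vaccination, by source:**

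| Source | MVA-BN dose 1 | MVA-BN dose 2 | ACAM2000, Group 1 | ACAM2000, Group 2 |
|---|---|---|---|---|
| Visit lists (site unhealed), days | 28-30 | 15 | 28-30 | 28-30, plus a second extension with no stated end |
| Schedule tables, days | 15 | 15 | 28-30 | 28-30 |
| General text, last diary day | Day 84 (82-86) | Day 56 (53-59) | Day 28 (27-29) | Day 28 (27-29) |
| SAP table label, days | 15 | 15 | 15 | 15 |

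Arithmetic:
- Extension returned at the visit 27-29 days after vaccination: 27 + 1 = 28 to 29 + 1 = 30 inclusive days.
- General text, dose 1 to Visit 10: 55 + 27 = 82, nominal 56 + 28 = 84, 57 + 29 = 86.
- General text, dose 2 to Visit 10: 55 − 29 + 27 = 53, nominal 56 − 28 + 28 = 56, 57 − 27 + 29 = 59.

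**Reading across the rows.** None of the three protocol sources gives a common window. By the visit lists, Days 15-28 (28 − 15 + 1 = 14 days) are covered on 0 of 14 days after dose 2 and on 14 of 14 after ACAM2000. By the general text the order reverses: the two MVA-BN doses have the longer windows.

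**What the SAP does with this.** Take a reaction that is last present after Day 14 but before Day 28. With an extension it has an end date, and SAP Section 3.8.3 gives it a duration. With a diary that ended on Day 14 it is ongoing on the last diary day and gets no duration, unless an end date comes from another source. By the visit lists, the first case is ACAM2000 with an unhealed site and the second is MVA-BN dose 2.

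**Does the 15-day label settle it?** Not clearly. SAP Section 3.8.2 applies the 15 days to onset: a listed symptom that begins later becomes unsolicited. Section 3.10.9 counts subjects who develop a reaction within the 15 days. The duration formula runs to the last day of the symptom, with no Day 14 cutoff. Nothing says whether extension data enter.

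**The case against.** The best defence is that the requirement exists and only a checklist line is missing. This is largely right. A reader might infer from the Visit 6 list that nothing need be recorded after Day 14 of the second MVA-BN dose, or that persisting general symptoms have no form at all. The documents do not support either inference: Sections 4.2.2, 8.1.3.2 and 8.2.6 and footnote 6 cover any persisting symptom after any dose. What remains is that the listed procedures neither issue nor collect the form, and that the handout trigger is narrower than the rule.

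End dates can also come from elsewhere. Visit 7 includes adverse event recording and examination of the vaccination site, and Section 8.2.6 allows ongoing reactions to be measured or examined. So an end date need not be missing, though it would rest on recall and not on a daily entry.

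A reader might further infer that Group 2 is followed past Day 28 and Group 1 is not. That rests on the Group 2 Visit 4 list alone. Footnote 7, Section 4.2.2 and Section 8.2.6 all stop at Visit 4, the schedule marks no handout there, and Section 4.2.4 treats both groups alike by asking for the date the scab came off.

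Finally, a reader might conclude that durations must differ between periods by construction. If the analysis cuts every duration at Day 14, as the endpoint definition and table label could imply, the extensions do not matter. The effect is therefore conditional on a choice that the SAP has not stated.

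**Conclusion.** The contradiction is established: the general text, the visit lists and the schedule tables give three different sets of diary windows, and the second Group 2 extension conflicts with the Visit 4 stop and has no collection visit. The effect on results is conditional. If extension data enter the duration tables, the windows differ by vaccination under every reading of the protocol. If sites follow the visit lists, the longest dose-2 reactions may have no diary end date and drop out of the summary.

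The direction of any distortion depends on which text sites follow. Its size depends on the share of reactions lasting beyond Day 14, which the documents do not give. Durations are summarised descriptively and secondary comparisons carry no confirmatory weight (Protocol Section 9.6). Neither co-primary endpoint is affected. It is still worth correcting, because duration is part of a named endpoint and the correction is cheap.

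**What to change.** **Protocol.** List the extension handout at Visits 3, 6 and 9 for Group 1 and at Visit 3 for Group 2. List review and collection at Visits 4, 7 and 10 for Group 1 and at Visit 4 for Group 2. Use one trigger throughout: any solicited local or general symptom still ongoing, or a site not healed. Bring footnote 7 into line with Section 8.1.3.2, and state the same stop for each vaccination in Sections 4.2.2 and 8.2.6 and footnote 6. Delete the second Group 2 extension at Visit 4, since Section 4.2.4 already obtains the date of scab loss in both groups.

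**SAP.** Carry the changes into Tables 1 and 2. State one duration window for every vaccination period and say whether extension data enter. Report reactions ongoing at the end of the window as a count (censored) beside the duration summary, and do not leave them out. If the window ends at the visit around Day 28, note that Visit 7 falls 26 to 30 days after Visit 4 (55 − 29 and 57 − 27), so earlier visits need a stated rule.

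**Cost.** A minor amendment that uses an existing form at existing visits, and a little more diary work for subjects with persisting symptoms.

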**Visit 7 (Visit 1 + 55-57 days)**

The following tasks will be performed

- Targeted physical examination, including auscultation of heart and lungs; see [Section 8.2.3](#) for more details
- Evaluation of vital signs
- Questions on cardiac signs and symptoms
- Review of prior/concomitant medications
- Counseling on avoidance of contact spread, HIV infection and pregnancy
- Examination of vaccination site
- Assessment of axillary and supraclavicular lymphadenopathy, see [Section 8.2.3](#) for more details
- Recording of AEs/SAEs/AESIs
- Urine or serum pregnancy test (5 ml, if applicable)
- Blood draw (serum collection) for antibody analysis (16 ml)
- Check of safety laboratory results obtained at Visit 6

Tasks mentioned above must always be performed prior to vaccination.

- Administration of one dose of ACAM2000®

### Visit 7 (Visit 1 + 55-57 days)

The following tasks will be performed (or repeated) after vaccination:

- Subject observation by clinical trial site staff for at least 30 minutes after vaccination
- Handout of memory aid
- Recording of immediate AEs/SAEs/AESIs
- Examination of the vaccination site and/or the area around the bandage for skin reactions (approximately 30 minutes after vaccination)
- Bandage application and handout of clinical trial specific Care Kits

**Temporary deferral of vaccination:** If an acute illness is present at the time scheduled for the vaccination, the subject may be vaccinated at a later date within the foreseen time window. The vaccine can be administered to persons with a minor illness such as diarrhea, mild upper respiratory infection, or any other mild condition with or without low-grade febrile illness, i.e. oral temperature < 100.4°F (< 38.0°C).

### Visit 8 (Visit 7 + 6-8 days)

The following tasks will be performed

- Targeted physical examination, including auscultation of heart and lungs (if clinically indicated); see [Section 8.2.3](#) for more details
- Evaluation of vital signs
- Counseling on avoidance of contact spread, HIV infection and pregnancy
- Assessment of axillary and supraclavicular lymphadenopathy; see [Section 8.2.3](#) for more details
- Recording of AEs/SAEs/AESIs
- Examination of vaccination site
- Photo of vaccination site
- Bandage application/change
- Review of memory aid

### Visit 9 (Visit 7 + 13-15 days)

The following tasks will be performed

- Targeted physical examination, including auscultation of heart and lungs; see [Section 8.2.3](#) for more details
- Evaluation of vital signs
- Perform ECG
- Questions on cardiac signs and symptoms
- Review of prior/concomitant medications
- Counseling on avoidance of contact spread, HIV infection and pregnancy
- Examination of the vaccination site
- Photo of vaccination site
- Bandage application/change
- Assessment of axillary and supraclavicular lymphadenopathy; see [Section 8.2.3](#) for more details
- Recording of AEs/SAEs/AESIs
- Collection of the memory aid handed out at Visit 7 and review with subject
- If vaccination site has not yet fully healed then a memory aid extension would be handed out
- Blood draw for safety laboratory (CBC with differential, total bilirubin, Alk Phos, AST, ALT, creatinine, sodium, potassium and calcium, 10ml) including troponin I testing

### Visit 10 (Visit 7 + 27-29 days)

The following tasks will be performed

- Targeted physical examination, including auscultation of heart and lungs; see [Section 8.2.3](#) for more details
- Questions on cardiac signs and symptoms
- Review of prior/concomitant medications
- Counseling on avoidance of contact spread and HIV infection

**Visit 10 (Visit 7 + 27-29 days)**

- Examination of the vaccination site
- Bandage application/change
- Assessment of axillary and supraclavicular lymphadenopathy; see [Section 8.2.3](#) for more details
- Recording of AEs/SAEs/AESIs
- Urine or serum pregnancy test (5 ml, if applicable)
- Blood draw (serum collection) for antibody analysis (16 ml)
- If a memory aid extension had been provided at Visit 9 then a review of memory aid extension should be conducted and the memory aid collected

